### 5.6.3 Disallowed medication

**Table 6 Disallowed medications**

Treatment to be withdrawn before Visit 2 until completion of the study follow up visit (Visit 7)	Time limits prior to Visit 2
Oral, parenteral and depot parenteral glucocorticosteroids (GCS)	4 weeks
Intramuscular or intra-articular depot steroids	3 months
Antibiotics (systemic and nebulised)	4 weeks
Immunomodulatory agents	8 weeks
Any medication containing ephedrine	24 hours
CYP2B6 substrates	4 weeks
Including but not limited to: bupropion, cyclophosphamide, efavirenz, ifosfamide, selegiline, alfentanil, nevirapine, propofol, tamoxifen, valproic acid, artemisinin, pethidine, modafinil, sertraline, thiotepa.	
Permeability glycoprotein (PgP) substrates	4 weeks
Including but not limited to: quinidine, tacrolimus, ivermectin, colchicines, etoposide, doxorubicin, vinblastine, protease inhibitors, non-nucleoside reverse transcriptase inhibitors, cyclosporin, digoxin	
Warfarin or other coumarins	4 weeks
All herbal medications	3 weeks

In addition, treatment with any other drug which, in the opinion of the investigator, is likely to compromise patient safety or interfere with the objectives of the study is disallowed from Visit 1 and throughout the study.

### 5.7 Treatment compliance

The administration of all study drugs (including investigational products) should be recorded in the appropriate sections of the eCRF and the drug accountability/dispensing record.

Investigational product accountability will be performed at Visits 3, 4, 5 and 6. Intake of investigational product will be recorded daily by the patient in their diary cards, this data will

be used by clinic staff to record the date/time of dose and fasting status in the eCRF on the day of clinic visits and the 2 previous days and to support compliance monitoring.

### 5.7.1 Accountability

The study drug provided for this study will be used only as directed in the study protocol.

The study personnel will account for all study drugs dispensed to and returned from the patient.

The destruction of used and unused study drug should preferably be done by the study site. The study site personnel/AZ monitor will account for all study drugs received at the site, unused study drugs and for appropriate destruction. If destruction at the study site is not possible, the monitor will be responsible for organising destruction in accordance with local requirements and will account for all received study drugs and return of all unused study drugs.

All certificates of delivery, destruction and return should be signed.

## 5.8 Discontinuation of investigational product

Patients may be discontinued from investigational product (IP) in the following situations:

- Patient decision. The patient is at any time free to discontinue treatment, without prejudice to further treatment
- Adverse Event
- Severe non-compliance to study protocol
- Safety reasons (risk to patients as judged by the investigator and/or AstraZeneca)
- Eligibility criteria not fulfilled
- Patient lost to follow-up

In addition to the above, the Investigator shall discontinue IP in the following situations:

- Development of study-specific withdrawal criteria:
  - Clinically significant lower respiratory tract infection as judged by the investigator
  - Patient has haematological changes which have not recovered on repeat sample taken after 2.30 pm and within 48 hours defined as one or more of:
    - local laboratory confirmed neutrophil count  $<1.0 \times 10^9/L$  (see below)

- local laboratory confirmed leucocyte count  $<2.0 \times 10^9/L$  (see below)
- Patient has hepatic toxicity defined as one or more of:
  - confirmed ALT or AST increase  $>3 \times ULN$
  - confirmed isolated total bilirubin increase  $>2 \times ULN$
  - confirmed ALT or AST increase  $>2 \times ULN$  concurrent with an increase in total bilirubin to  $>1.5 \times ULN$
  - any pattern of liver function test (LFT) abnormalities giving cause for concern in the opinion of the Investigator

These events must be followed up as appropriate for the patient.

- Confirmed serum creatinine  $>1.5 \times ULN$
- COPD exacerbation requiring treatment with antibiotics, and/or systemic glucocorticosteroids, and/or hospitalisation
- Other reasons:
  - Pregnancy (refer to Section 13.3)
  - Treatment code prematurely broken by the investigator
- Death.

AstraZeneca are proposing to discontinue patients from study medication if they have a high likelihood of having a sustained ANC below  $1 \times 10^9/L$ . AstraZeneca have defined “sustained” as a period greater than 24 hours but less than 48 hours. Patients who are found to have an ANC below  $1 \times 10^9/L$  or a leucocyte count below  $2 \times 10^9/L$  (according to local laboratory measurements) at any of their clinic visits will have a repeat blood sample taken in the afternoon of the following day (after 2:30 pm). The second test is in the afternoon because the circulating neutrophil numbers then are naturally higher than in the morning. Neutrophil numbers normally vary in a diurnal pattern, the numbers being lowest at around 8:00 am and highest around 8:00 pm. Diurnal fluctuations in the ANC/leucocyte count are still present in patients who have taken AZD5069.

If on repeat examination, the ANC/leucocyte count stopping criteria are still met, despite the second sample being taken when neutrophil levels are usually higher than in the morning, AZD5069 therapy will be discontinued. This is because AstraZeneca will assume that the ANC/leucocyte count is sustained even though the counts will not have been determined at the highest point of its daily cycle. Site staff should ensure that no patient takes more than 4 doses of study drug from the time of their initial abnormal blood test. Patients will be

informed by site staff (at enrolment and screening) that they should not take the morning dose of the study drug 2 days after the first abnormal blood test without first obtaining consent from the clinic (by telephone on the morning of the third day) that it is appropriate to do so.

Subjects who have missed and/or forgotten more than 3 consecutive doses should be referred to the AstraZeneca Study Physician for assessment as to whether the interruption in the Investigational Product constitutes discontinuation.

If a patient is withdrawn because of low neutrophil counts, the Investigator will monitor the blood count the following day and then at least every other day after that until the neutrophil numbers are within the local laboratory's reference range.

Specific reasons for discontinuing a patient from the genetic research are detailed in Appendix D.

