### 6.4.9 Lung function measurements

Lung function tests will be measured by spirometry at the clinic at Visits 1.1, 2 and 3 to 7 inclusive. The tests being performed are FEV1, FVC, SVC, IC, FEF25-75%, pre- and 30 minutes post-bronchodilator.

The measurements at Visit 2 will be performed pre-dose, and subsequent measurements will be performed at the same time of day throughout the study  $\pm 2$  hours relative to the time at baseline (Visit 2). A record of the measurements must be made in the patient's notes and results recorded in the eCRF. All printouts should be signed, dated, and marked with study code, enrolment/randomisation code, date and time of measurement and visit number.

The initial assessments should be performed prior to the administration of any bronchodilators and should be performed with the patient in an upright, seated position, having rested for 15 minutes. See Section [5.1](#) for restrictions around the spirometry tests.

Measurements should be performed according to American Thoracic Society/European Respiratory Society (ATS/ERS) guidelines ([Miller et al 2005a](#), [Miller et al 2005b](#)). In general:

- An electronic spirometer should be used and the same apparatus used for each patient at the centre
- The centre will be responsible for calibrating and recording the calibration of the spirometer according to the recommendations of the manufacturer. Unless otherwise advised, this should be on a daily basis and where there is a significant fluctuation in temperature or barometric pressure.

All calibration reports should be signed, dated and filed in the Investigator Site File (ISF). If a calibration report cannot be printed, the results should be documented in writing in the ISF.

- Lung function measurements may be carried out in the morning or in the afternoon; however, lung function measurements should be carried out at the same time of day ( $\pm 2$  hours) for each individual patient throughout the study
- The patient should be sitting with his/her head level and tight clothing should be loosened
- The patient should perform the manoeuvre with a nose clip

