#### 6.4.10 COPD Exacerbations

A COPD exacerbation is defined as worsening in COPD requiring treatment with one or more of the following:

- systemic antibiotics (oral or parenteral)
- systemic GCS (oral or parenteral)
- Emergency Room treatment
- hospitalisation.

The start date is defined as the first day of hospitalisation/emergency room treatment or the first day of systemic GCS or antibiotic treatment. The end date is defined as the last day of hospitalisation/emergency room treatment or the last day of systemic GCS or antibiotic treatment. If the same exacerbation includes both hospitalisation/emergency room treatment and systemic GCS/antibiotic treatment, the start and end dates are the first and last day that either criteria is fulfilled. If hospitalisation was prolonged for reasons other than COPD

exacerbation, then the exacerbation end date should be determined by the Investigator. One day without any criteria for fulfilment of an exacerbation is required to start to count a new exacerbation.

Exacerbations should be recorded as AEs in the eCRF.

Patients who experience a COPD exacerbation should be discontinued from investigational product, refer to Section 5.8.

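### The exacerbation stopping rule in Section 5.8 does not match Section 6.4.10, which refers to it; a smaller misalignment affects the timing of the neutrophil repeat within Section 5.8

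*Protocol*

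**What the plan says.** **Exacerbations.** The study-specific criteria in Protocol Section 5.8 are introduced by "In addition to the above, the Investigator shall discontinue IP in the following situations", so they are mandatory. The exacerbation entry reads "COPD exacerbation requiring treatment with antibiotics, and/or systemic glucocorticosteroids, and/or hospitalisation".

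Section 6.4.10 opens with "A COPD exacerbation is defined as worsening in COPD requiring treatment with one or more of the following" and lists four items: systemic antibiotics (oral or parenteral), systemic glucocorticosteroids, "Emergency Room treatment", and hospitalisation. It ends with "Patients who experience a COPD exacerbation should be discontinued from investigational product, refer to Section 5.8". It also requires exacerbations to be recorded as adverse events.

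**Neutrophils.** The low-count entry in the Section 5.8 list asks for no recovery on a repeat drawn later than 2.30 pm and no more than 48 hours on. It points the reader to the text below. That text, still in Section 5.8, defines a sustained low count "as a period greater than 24 hours but less than 48 hours" and says that patients with a low count at any clinic visit "will have a repeat blood sample taken in the afternoon of the following day (after 2:30 pm"). It says the sponsor will then assume that a low repeat is sustained.

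**The concern.** Section 6.4.10 sends the reader to Section 5.8 for the stopping rule, and the rule found there covers a different set of patients. Two sites following the protocol carefully could treat the same patient differently, one stopping treatment because 6.4.10 says so and the other finding no mandatory criterion in 5.8.

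This bears on the primary objective. Adverse events are a primary safety variable (Table 1), and Section 12.2.3 summarises the patients with adverse events that led to withdrawal. Section 12.2.1 includes a withdrawn patient only up to discontinuation, so the stopping decision also determines how much of that patient's data enters the summaries.

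The neutrophil texts raise a smaller question. The definition of a sustained fall requires more than 24 hours, but no sentence requires 24 hours between the two samples that trigger stopping.

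**Working it through.** **1. Exacerbation triggers side by side**

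| Trigger | Section 5.8 (mandatory list) | Section 6.4.10 (definition, then stop) |
|---|---|---|
| Systemic antibiotics | yes | yes |
| Non-systemic antibiotics, e.g. nebulised | could be read as included, since the route is not limited | no |
| Systemic glucocorticosteroids | yes | yes |
| Emergency room treatment alone | not listed | yes |
| Hospitalisation | yes | yes |

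The four triggers in 6.4.10 give 2^4 − 1 = 15 non-empty combinations. Fourteen contain at least one of antibiotics, systemic glucocorticosteroids or hospitalisation and are also covered by 5.8. One, emergency room only, is not. This counts logical cases and is not a frequency.

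Can hospitalisation in 5.8 be read to include emergency room care? The protocol points the other way. Section 6.4.10 lists the two separately, and Appendix B says outpatient emergency room treatment does not by itself make an event serious, whereas in-patient hospitalisation does (Section 6.4.2).

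Is the antibiotic route a real distinction? Table 6 in Section 5.6.3 names systemic and nebulised antibiotics separately, so the protocol itself uses it. The mismatch is weaker in this direction. A reader who applies the 6.4.10 definition to the word exacerbation in 5.8 would not count a patient given only nebulised antibiotics. That is why such a patient could, rather than does, fall under 5.8.

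**2. Interval between the two neutrophil samples**

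Inputs: the repeat is on the following day, at 14:30 at the earliest (Section 5.8). The time of the first sample, t (24-hour clock, in hours), is not given. Section 6.4.9 says "Lung function measurements may be carried out in the morning or in the afternoon", and Section 3.1 schedules visits around spirometry, so an afternoon first sample is possible. The times below are assumptions, taken over an assumed clinic day of 08:00 to 18:00.

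Shortest interval = 24 + (14.5 − t).

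| First low sample (assumed) | Shortest interval to next-day repeat |
|---|---|
| 08:00 | 24 + 14.5 − 8 = 30.5 h |
| 12:00 | 24 + 14.5 − 12 = 26.5 h |
| 14:30 | 24 + 14.5 − 14.5 = 24.0 h |
| 16:00 | 24 + 14.5 − 16 = 22.5 h |
| 18:00 | 24 + 14.5 − 18 = 20.5 h |

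The interval can be below 24 hours only when t is later than 14:30, and then only for an early repeat. For a 16:00 first sample, a repeat at 18:00 the next day gives 26.0 h. With morning first samples the next-day rule always exceeds 24 hours.

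**The case against.** **On exacerbations.** The gap is narrow, because it needs emergency room care with no antibiotics, no systemic glucocorticosteroids and no admission. Section 5.8 also permits stopping for an adverse event or for safety reasons, and nothing in it says such a patient must continue. An investigator can therefore satisfy both sections by stopping. This stands as a limit on size, but it does not remove the mismatch: the discretionary grounds permit stopping, whereas the list meant to carry the mandatory rule lacks one of its triggers.

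A reader might also infer that the count of exacerbations as adverse events depends on the section read. It does not. Section 6.4.10 gives one definition and requires every exacerbation to be recorded whether or not treatment stops. Only withdrawals, and the adverse events attributed to them, can differ.

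**On neutrophils.** A reader might infer a second contradiction of equal weight, or that a repeat on the same day would do. The documents do not support either. Both texts are in Section 5.8, the list refers to the text below it, and that text fixes the repeat to the following afternoon, inside the 48-hour window. It also presents the repeat as an assumed proxy for a count with a high likelihood of being sustained, not as proof of duration. Nor does the rationale for an afternoon repeat fail outright: it compares afternoon with morning counts, and the second sample is always after 2:30 pm. For an afternoon first sample that comparison simply offers less reassurance.

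Finally, the modelled proportion of healthy subjects in Section 3.2.4 might be taken as a planned withdrawal rate against which to size the problem. It is dose rationale for a neutrophil fall in healthy subjects. It is not a planned rate in these patients and is unrelated to exacerbations.

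**Conclusion.** The exacerbation point holds. Sections 5.8 and 6.4.10 give different answers for a patient treated only in the emergency room, and possibly for one treated only with non-systemic antibiotics. The consequence is confined to who is withdrawn, how adverse events leading to withdrawal are counted, and how long such a patient contributes data. Its numerical size cannot be derived, because the documents give no frequency for either case. The protocol makes no sample-size calculation (Section 12.3), so no design figure changes.

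The neutrophil point is minor. The window in the list, the definition of sustained and the next-day repeat fail to align only when the first low sample is drawn after 14:30. The documents allow such a draw but do not establish that it will happen. The 22.5 h figure rests on an assumed 16:00 draw and the earliest permitted repeat.

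Neither point implies a view on which clinical rule is right.

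**What to change.** Reconcile Sections 5.8 and 6.4.10 so that both use one exacerbation wording, covering the same treatments and the same antibiotic routes, and so that the reference from 6.4.10 leads to a matching rule. The sponsor should decide which wording applies; none is proposed here.

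Within Section 5.8, make the window in the list, the definition of a sustained low count and the timing of the repeat agree for first samples drawn at any time of day. In the report, give the actual elapsed time between the two samples for each patient with a low count.

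The cost is a wording change to two sections of the protocol, plus the clock times of the first and repeat samples. It is assumed, not stated, that existing laboratory records can supply those times. No change to sample size, visits or analysis method is needed.

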### **5.8.1 Procedures for discontinuation of a patient from investigational product**

A patient that decides to discontinue IP will always be asked about the reason(s) and the presence of any adverse events. If possible, they will be seen and assessed by an investigator(s).

If a patient discontinues after randomisation, they should be asked to attend the end of treatment visit (Visit 6) and all assessments at Visit 6 should be carried out unless the patient does not wish to do so. The patient should then be asked to attend the follow-up visit (Visit 7). The reason for discontinuation will be recorded in the eCRF. Adverse events will be followed up (see Sections 6.4.3 and 6.4.4); diary cards and all study drugs should be returned by the patient.

If a patient is withdrawn from study, see Section 5.9.

## **5.9 Withdrawal from study**

Patients are at any time free to withdraw from study (investigational product and assessments), without prejudice to further treatment (withdrawal of consent). Such patients will always be asked about the reason(s) and the presence of any adverse events. If possible, they will be seen and assessed by an investigator. Adverse events will be followed up (see Sections 6.4.3 and 6.4.4); diary cards and all study drugs should be returned by the patient.

In the event that a patient cannot return for Visit 6 (eg, because of death, or because they are lost to follow up), this will be recorded in the eCRF. Adverse events will be followed up to the last point of contact.

Withdrawn patients will not be replaced.

## 6. COLLECTION OF STUDY VARIABLES

### 6.1 Recording of data

The Rave Web Based Data Capture (WBDC) system will be used for data collection and query handling.

The investigator will ensure that data are recorded in the eCRF as specified in the study protocol and in accordance with the instructions provided. The investigator ensures the accuracy, completeness and timeliness of the data recorded and of the provision of answers to data queries according to the Clinical Study Agreement (CSA). The investigator will sign the completed eCRF. A copy of the completed eCRF will be archived at the study site.

The patient will be instructed to maintain a paper diary throughout the study period (Visits 1-7), to record administration of study drug, fasting status, concomitant medications, AEs and twice daily body temperature measurements (orally morning and evening). A new diary card will be given to the patient at each clinic visit. Patient-recorded daily oral body temperature measurements will not be entered onto the WBDC system but if a temperature above 38.1°C is recorded this will be reported as an AE (fever) (see Section 6.4). Data collected on the diary cards will not be entered directly into the eCRF but will be reviewed by site staff to enable entry of dosing information on selected days, concomitant medications and AEs. A copy of the diary cards will be archived at the study site with the source data.

### 6.2 Data collection and enrolment

Investigators should refer to the study plan in [Table 3](#) for a detailed list of study procedures and assessments to be performed at screening and throughout the study period.

At Visit 1 patients will sign the informed consent form prior to any study procedure or restriction being applied and will be assigned a unique enrolment code (see Section 5.2). Patients will then attend the clinic for Visit 1.1 and will be screened and evaluated for eligibility to enter the study. The following assessments will be performed, with data being captured in the eCRF as appropriate:

- Demographic data
- Medical and surgical history
- COPD history
- Smoking history
- Height and weight
- Physical examination
- Vital signs

- Body temperature
- Safety bloods (haematology and clinical chemistry)
- Urinalysis
- Leucocyte count (analysed at local laboratory)
- Pregnancy test for all female patients
- 12-lead ECG
- Pre- and post-bronchodilator FEV1, FVC, SVC, IC and FEF25-75%
- Concomitant medications
- AEs.

In addition to the weekly clinic visits, clinic staff will also contact patients twice weekly via telephone in order to monitor any AEs, assess general health status, ensure that the patients are without fever and to ascertain whether an additional clinic visit is required. The date of the twice weekly telephone contact visits will be recorded on the WBDC system.

### 6.2.1 Follow-up procedures

Investigators should refer to the study plan in [Table 3](#) for a detailed list of study procedures and assessments to be performed at the follow-up visit (Visit 7).

The following assessments will be performed and recorded in the eCRF at this visit:

- Weight
- Concomitant medications
- AEs
- Physical examination
- Vital signs
- Body temperature
- Safety bloods (haematology and clinical chemistry)
- Urinalysis
- Leucocyte count

- Pregnancy test for all female patients
- 12-lead ECG
- Pre- and post-bronchodilator FEV1, FVC, SVC, IC and FEF25-75%.

### **6.3 Efficacy (Not applicable)**

Not applicable.

### **6.4 Safety**

The Principal Investigator is responsible for ensuring that all staff involved in the study are familiar with the content of this section.

#### **6.4.1 Definition of adverse events**

An adverse event is the development of an undesirable medical condition or the deterioration of a pre-existing medical condition following or during exposure to a pharmaceutical product, whether or not considered causally related to the product. An undesirable medical condition can be symptoms (eg, nausea, chest pain), signs (eg, tachycardia, enlarged liver) or the abnormal results of an investigation (eg, laboratory findings, electrocardiogram). In clinical studies, an AE can include an undesirable medical condition occurring at any time, including run-in or washout periods, even if no study treatment has been administered.

The term AE is used to include both serious and non-serious AEs.

